APPENDIX IV: INTERVENTION – ACCEPTED DA – PATIENT FOLLOW-UP SURVEY

You have been given a booklet to complete for this study. The booklet contains some questions related to visits with your surgeon, about what was important to you when you thought about your decision for breast cancer surgery, and any materials that helped you make a decision. Your answers will help us to better understand how to support patients in making their decision about breast cancer surgery.

1. Directions on how to complete each set of questions are written on the top of each set.
2. You will be given the site coordinator's name and telephone number. You can call any time with any concerns or questions.
3. It is very important that you return the booklet to us.
4. Please hand the completed survey to the site coordinator or use the stamped and addressed envelope provided to mail the completed survey to the site coordinator. If we do not hear from you in the next week, we will contact you again.

Thank you for taking the time to help us.

INTERVENTION ARM – ACCEPTED DECISION AID**PATIENT FOLLOW-UP (T2) SURVEY**

Thank you for taking the time to complete this survey. This survey is about 50 questions and should take about 10 to 20 minutes to complete.

The first set of questions contains items that are related to visits with a surgeon. Please answer each statement to the best of your ability.

	Not at all confident					Very confident (5)
	(1)	(2)	(3)	(4)		
1. How confident are you in your ability to know what questions to ask a surgeon?						
2. How confident are you in your ability to get a surgeon to answer all of your questions?						
3. How confident are you in your ability to make the most of your visit with a surgeon?						
4. How confident are you in your ability to get a surgeon to take your chief health concerns seriously?						
5. How confident are you in your ability to get a surgeon to do something about your chief health concern?						

The second set of questions contains items that are related to your recent visit with your surgeon. Surgeons have different styles in how they interact with patients and we would like to know more about how you felt about your visit with your surgeon. Please indicate how much you agree or disagree with each statement. Please answer to the best of your ability.

	Strongly disagree (1)			Neutral (4)			Strongly agree (7)	
	(2)	(3)	(5)	(6)				
6. I feel that my surgeon has provided me choices and options.								
7. I feel understood by my surgeon.								
8. I am able to be open with my surgeon at our meetings.								
9. My surgeon conveys confidence in my ability to make treatment choices.								
10. I feel that my surgeon accepts me.								
11. My surgeon has made sure I really understand about my condition and what I need to do.								
12. My surgeon encourages me to ask questions.								
13. I feel a lot of trust in my surgeon.								
14. My surgeon answers my questions fully and carefully.								
15. My surgeon listens to how I would like to do things.								
16. My surgeon handles people's emotions very well.								
17. I feel that my surgeon cares about me as a person.								
18. I don't feel very good about the way my surgeon talks to me.								
19. My surgeon tries to understand how I see things before suggesting how to do things.								
20. I feel able to share my feelings with my surgeon.								

The next set of questions asks about some facts that surgeons think are important for patients to know about breast cancer. The correct answer to each question is based on medical research. Please answer to the best of your ability.

21. For most women with early breast cancer, how much would waiting a few weeks to make a treatment decision affect their chances of survival?

- A little or not at all
- A lot
- Some

22. With treatment, about how many women diagnosed with early breast cancer will eventually die of breast cancer?

- About half will die of breast cancer
- Most will die of breast cancer
- Most will die of something else

23. After which treatment is it more likely that women will need to have another operation to remove more tumor cells?

- Lumpectomy
- Mastectomy
- Equally likely for both

24. On average, which women with early breast cancer live longer?

- Women who have a mastectomy
- Women who have a lumpectomy and radiation
- There is no difference

25. On average, which women have a higher chance of having cancer come back in the breast that has been treated?

- Women who have a mastectomy
- Women who have a lumpectomy and radiation
- There is no difference

We are interested in what was important to you when you made the decision about breast cancer surgery. We asked you these same questions before you met with your surgeon, and are asking again to see if anything has changed. Please mark on a scale from 0 to 10, how important were each of the following to you as you make your decision about surgery.

How important was it to you to . . .

	Not at all important										Extremely Important
26. keep your breast?	0	1	2	3	4	5	6	7	8	9	10
27. remove your entire breast to gain peace of mind?	0	1	2	3	4	5	6	7	8	9	10
28. avoid having radiation	0	1	2	3	4	5	6	7	8	9	10

29. (*Now that your clinic visit is over, if you currently have a preference to treat your early stage breast cancer*), which treatment do you prefer?

- I am not sure
- Lumpectomy and radiation
- Lumpectomy only
- Mastectomy
- Other surgery

Other surgery: _____

30. Do you feel sure about the best choice for you?

- Yes
- No

31. Do you know the benefits and risks of each option?

- Yes
- No

32. Are you clear about which benefits and risks matter most to you?

- Yes
- No

33. Do you have enough support and advice to make a choice?

- Yes
- No

You received a link to a website from your clinic prior to seeing your surgeon. The next questions ask about how this material helped you prepare to meet with your surgeon and make a decision for breast cancer surgery.

34. Did you review the website sent to you after seeing your surgeon?

- Yes
- No

(If yes), how much time did you spend reviewing the website?

- Less than 15 minutes
- 15 - 60 minutes
- More than 1 hour

35. After your initial phone call when clinic staff offered you the website information, how important did you think it was for you to review the website sent to you?

- Very important
- Neither important or unimportant
- Not at all important

36. Why did you think it was important or not important for you to review the website?

37. Did you review the website sent to you at any time?

- Yes, I reviewed the website (either before or after seeing the surgeon).
- No, I did not review the decision aid.

If you answered “Yes” to questions #34 or #37, please continue directly to question 38.

If you answered “No” to questions #34 and #37, please go directly to question #51.

	Not at all	A little	Somewhat	Quite a bit	A great deal
38. Did the website help you recognize that a decision needs to be made?	1	2	3	4	5
39. Did the website prepare you to make a better decision?	1	2	3	4	5
40. Did the website help you think about the pros and cons of each option?	1	2	3	4	5
41. Did the website help you think about which pros and cons are most important?	1	2	3	4	5
42. Did the website help you know that the decision depends on what matters most to you?	1	2	3	4	5
43. Did the website help you organize your own thoughts about the decision?	1	2	3	4	5
44. Did the website help you think about how involved you want to be in this decision?	1	2	3	4	5
45. Did the website help you identify questions you want to ask your surgeon?	1	2	3	4	5
46. Did the website prepare you to talk to your surgeon about what matters most to you?	1	2	3	4	5
47. Did the website prepare you for a follow-up visit with your surgeon?	1	2	3	4	5

48. Where did you review the website? Check all that apply.

- On my own computer at home
- On a computer at my family or friend's home
- On my own tablet or mobile phone
- On my family or friend's tablet or mobile phone
- On a public computer (ex. library)
- On a iPad in clinic
- Other

(If other), specify _____

49. Did anyone else review the website? (Either with you or you sending them the link)

Yes

No

(If yes), who? Check all that apply.

Partner/spouse

Family member

(If family member), specify _____

Friend

Other

(If other), specify _____

50. Did you have any trouble opening or using the website?

Yes

No

(If yes), what was hard about it?

The following questions are for all patients, regardless of whether they did and did not review the website sent to them from the clinic.

51. Did you like getting the website sent to you by email?

Yes

No

(If no), what did you not like about it?

52. What do you think would be the best format for you to receive and review information from the clinic?

- Paper version
- Computer-based version
- DVD-based version
- Other

(If other), specify _____

53. If the clinic continued to send web-based material prior to the first appointment with the surgeon, what would be the best way to receive this material?

- By email
- By electronic medical record, such as using a patient portal (MyChart)
- By text
- By mail
- Other

(If other), specify _____

Below are some questions so we can learn a little more about you. This information will help us understand how decision making between the surgeon and patient may be differ between patients, and how to better support patients in making their decision about breast cancer surgery.

1. What is the **highest** level of school or degree you have completed?

- Some high school or less
- High school diploma or GED
- Vocational degree or some college
- College degree
- Graduate school degree or higher

2. Are you of Hispanic, Latino, or Spanish origin?

- Yes
- No

3. How would you describe your racial background?

- White or Caucasian
- Black or African American
- Asian
- American Indian or Alaska Native
- Native Hawaiian or other Pacific Islander
- Other

(If other), specify _____

4. What do you consider to be your primary language?

- English
- Spanish
- Other

(If other), specify _____

5. What is your current marital status?

- Single, never married
- Married or domestic partnership
- Widowed
- Divorced
- Separated

6. What is your household annual income?

- <\$25,000 per year
- \$25,000 - \$49,999 per year
- \$50,000 - \$99,999 per year
- >\$100,000 per year

APPENDIX V: INTERVENTION – DECLINED DA – PATIENT FOLLOW-UP SURVEY

You have been given a booklet to complete for this study. The booklet contains some questions related to visits with your surgeon, about what was important to you when you thought about your decision for breast cancer surgery, and any materials that helped you make a decision. Your answers will help us to better understand how to support patients in making their decision about breast cancer surgery.

1. Directions on how to complete each set of questions are written on the top of each set.
2. You will be given the site coordinator's name and telephone number. You can call any time with any concerns or questions.
3. It is very important that you return the booklet to us.
4. Please hand the completed survey to the site coordinator or use the stamped and addressed envelope provided to mail the completed survey to the site coordinator. If we do not hear from you in the next week, we will contact you again.

Thank you for taking the time to help us.

INTERVENTION ARM – DECLINED DECISION AID**PATIENT FOLLOW-UP (T2) SURVEY**

Thank you for taking the time to complete this survey. This survey is about 50 questions and should take about 10 to 20 minutes to complete.

The first set of questions contains items that are related to visits with a surgeon. Please answer each statement to the best of your ability.

	Not at all confident					Very confident (5)
	(1)	(2)	(3)	(4)		
1. How confident are you in your ability to know what questions to ask a surgeon?						
2. How confident are you in your ability to get a surgeon to answer all of your questions?						
3. How confident are you in your ability to make the most of your visit with a surgeon?						
4. How confident are you in your ability to get a surgeon to take your chief health concerns seriously?						
5. How confident are you in your ability to get a surgeon to do something about your chief health concern?						

The second set of questions contains items that are related to your recent visit with your surgeon. Surgeons have different styles in how they interact with patients and we would like to know more about how you felt about your visit with your surgeon. Please indicate how much you agree or disagree with each statement. Please answer to the best of your ability.

	Strongly disagree (1)			Neutral (4)			Strongly agree (7)	
	(2)	(3)	(5)	(6)				
6. I feel that my surgeon has provided me choices and options.								
7. I feel understood by my surgeon.								
8. I am able to be open with my surgeon at our meetings.								
9. My surgeon conveys confidence in my ability to make treatment choices.								
10. I feel that my surgeon accepts me.								
11. My surgeon has made sure I really understand about my condition and what I need to do.								
12. My surgeon encourages me to ask questions.								
13. I feel a lot of trust in my surgeon.								
14. My surgeon answers my questions fully and carefully.								
15. My surgeon listens to how I would like to do things.								
16. My surgeon handles people's emotions very well.								
17. I feel that my surgeon cares about me as a person.								
18. I don't feel very good about the way my surgeon talks to me.								
19. My surgeon tries to understand how I see things before suggesting how to do things.								
20. I feel able to share my feelings with my surgeon.								

The next set of questions asks about some facts that surgeons think are important for patients to know about breast cancer. The correct answer to each question is based on medical research. Please answer to the best of your ability.

21. For most women with early breast cancer, how much would waiting a few weeks to make a treatment decision affect their chances of survival?

- A little or not at all
- A lot
- Some

22. With treatment, about how many women diagnosed with early breast cancer will eventually die of breast cancer?

- About half will die of breast cancer
- Most will die of breast cancer
- Most will die of something else

23. After which treatment is it more likely that women will need to have another operation to remove more tumor cells?

- Lumpectomy
- Mastectomy
- Equally likely for both

24. On average, which women with early breast cancer live longer?

- Women who have a mastectomy
- Women who have a lumpectomy and radiation
- There is no difference

25. On average, which women have a higher chance of having cancer come back in the breast that has been treated?

- Women who have a mastectomy
- Women who have a lumpectomy and radiation
- There is no difference

We are interested in what was important to you when you made the decision about breast cancer surgery. We asked you these same questions before you met with your surgeon, and are asking again to see if anything has changed. Please mark on a scale from 0 to 10, how important were each of the following to you as you make your decision about surgery.

How important was it to you to . . .

	Not at all important										Extremely Important	
26. keep your breast?	0	1	2	3	4	5	6	7	8	9	10	
27. remove your entire breast to gain peace of mind?	0	1	2	3	4	5	6	7	8	9	10	
28. avoid having radiation	0	1	2	3	4	5	6	7	8	9	10	

29. (*Now that your clinic visit is over, if you currently have a preference to treat your early stage breast cancer*), which treatment do you prefer?

- I am not sure
- Lumpectomy and radiation
- Lumpectomy only
- Mastectomy
- Other surgery

Other Surgery: _____

30. Do you feel sure about the best choice for you?

- Yes
- No

31. Do you know the benefits and risks of each option?

- Yes
- No

32. Are you clear about which benefits and risks matter most to you?

- Yes
- No

33. Do you have enough support and advice to make a choice?

- Yes
- No

The next questions ask about any materials that helped you prepare to meet with your surgeon and make a decision for breast cancer surgery.

34. Did you review any information after seeing your surgeon?

- Yes
- No

If you answered “No” to question #34, please proceed directly to question #35.

(If yes), what types of information did you review after meeting your surgeon?

(If yes), how much time did you spend reviewing the information?

- Less than 15 minutes
- 15 - 60 minutes
- More than 1 hour

If you answered “Yes” to question #34, please proceed directly to Question #36.

If you answered “No” to question #34, please answer Question #35.

35. Did you review any information at any time?

- Yes, I reviewed information (either before or after seeing the surgeon).
- No, I did not review any information.

If you answered “Yes” to question #35, continue to question #36.

If you answered “No” to question #36, go directly to question #48.

	Not at all	A little	Somewhat	Quite a bit	A great deal
36. Did the information help you recognize that a decision needs to be made?	1	2	3	4	5
37. Did the information prepare you to make a better decision?	1	2	3	4	5
38. Did the information help you think about the pros and cons of each option?	1	2	3	4	5
39. Did the information help you think about which pros and cons are most important?	1	2	3	4	5
40. Did the information help you know that the decision depends on what matters most to you?	1	2	3	4	5
41. Did the information help you organize your own thoughts about the decision?	1	2	3	4	5
42. Did the information help you think about how involved you want to be in this decision?	1	2	3	4	5
43. Did the information help you identify questions you want to ask your surgeon?	1	2	3	4	5
44. Did the information prepare you to talk to your surgeon about what matters most to you?	1	2	3	4	5
45. Did the information prepare you for a follow-up visit with your surgeon?	1	2	3	4	5

46. Where did you review the information? Check all that apply.

- On my own computer at home
- On a computer at my family or friend's home
- On my own tablet or mobile phone
- On my family or friend's tablet or mobile phone
- On a public computer (ex. library)
- On a iPad in clinic
- Other

(If other), specify _____

47. Did anyone else review the information? (Either with you or you sending them the information)

- Yes
- No

(If yes), who? Check all that apply.

- Partner/spouse
- Family member

(If family member), specify _____

- Friend
- Other

(If other), specify _____

The following questions are for all patients, regardless of whether they did and did not review any materials to help make a decision about the type of breast cancer surgery to have.

48. Would you like to receive information from the clinic?

- Yes
- No

49. What do you think would be the best format for you to receive and review information from the clinic?

- Paper version
- Computer-based version
- DVD-based version
- Other

(If other), specify _____

50. If the clinic sent web-based material prior to the first appointment with the surgeon, what would be the best way to receive this information?

- By email
- By electronic medical record, such as using a patient portal (MyChart)
- By text
- By mail
- Other

(If other), specify _____

Below are some questions so we can learn a little more about you. This information will help us understand how decision making between the surgeon and patient may be differ between patients, and how to better support patients in making their decision about breast cancer surgery.

1. What is the **highest** level of school or degree you have completed?

- Some high school or less
- High school diploma or GED
- Vocational degree or some college
- College degree
- Graduate school degree or higher

2. Are you of Hispanic, Latino, or Spanish origin?

- Yes
- No

3. How would you describe your racial background?

- White or Caucasian
- Black or African American
- Asian
- American Indian or Alaska Native
- Native Hawaiian or other Pacific Islander
- Other

(If other), specify _____

4. What do you consider to be your primary language?

- English
- Spanish
- Other

(If other), specify _____

5. What is your current marital status?

- Single, never married
- Married or domestic partnership
- Widowed
- Divorced
- Separated

6. What is your household annual income?

- <\$25,000 per year
- \$25,000 - \$49,999 per year
- \$50,000 - \$99,999 per year
- >\$100,000 per year

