10.1.4.1 Preparatory Barriers

- Patients Expectations for Their Role in a SDM Encounter

Control Preferences Scale (baseline patient survey): The Control Preferences Scale (CPS) is validated survey instrument that was developed to measure patient's preferred and/or perceived roles in their health-care decision-making; it consists of a single item. The roles range from the individual making the treatment decision, through the individual making the decision jointly with the physician, to the physician making the decision.⁷⁷

Preparation for Decision Making Scale (follow-up patient survey): The ten-item Preparation for Decision Making (PrepDM) scale was developed to evaluate decision processes relating to the preparation of patients for decision making and dialoguing with their practitioners.⁷⁸ It has been demonstrated to be reliable and valid, and discriminates based on perceived usefulness of decision support tools.

- Patients' Knowledge about the Decision Faced:

"How informed do you feel?" (baseline patient survey): We will ask how informed patients feel about the surgical options for breast cancer before their consultation with the surgeon.

SURE Decisional Conflict Scale (follow-up patient survey): The 4-item SURE (Sure of myself; Understand information; Risk-benefit ratio; Encouragement) screening test was developed to help health professionals identify patients with clinically significant decisional conflict as quickly as possible.⁸¹

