We are interested in what was important to you when you made the decision about breast cancer surgery. We asked you these same questions before you met with your surgeon, and are asking again to see if anything has changed. Please mark on a scale from 0 to 10, how important were each of the following to you as you make your decision about surgery.

How important was it to you to . . .

	Not at all important										Extremely Important
26. keep your breast?	0	1	2	3	4	5	6	7	8	9	10
27. remove your entire breast to gain peace of mind?	0	1	2	3	4	5	6	7	8	9	10
28. avoid having radiation	0	1	2	3	4	5	6	7	8	9	10

29. (*Now that your clinic visit is over, if you currently have a preference to treat your early stage breast cancer*), which treatment do you prefer?

- I am not sure
- Lumpectomy and radiation
- Lumpectomy only
- Mastectomy
- Other surgery

Other surgery: _____

30. Do you feel sure about the best choice for you?

- Yes
- No

31. Do you know the benefits and risks of each option?

- Yes
- No

32. Are you clear about which benefits and risks matter most to you?

- Yes
- No

33. Do you have enough support and advice to make a choice?

- Yes
- No

The next questions ask about any materials that helped you prepare to meet with your surgeon and make a decision for breast cancer surgery.

34. Did you review any information after seeing your surgeon?

- Yes
- No

If you answered “No” to question #34, please proceed directly to question #35.

(If yes), what types of information did you review after meeting your surgeon?

(If yes), how much time did you spend reviewing the information?

- Less than 15 minutes
- 15 - 60 minutes
- More than 1 hour

If you answered “Yes” to question #34, please proceed directly to question #36.

If you answered “No” to question #34, please answer question #35.

35. Did you receive any information at any time?

- Yes, I reviewed information (either before or after seeing the surgeon).
- No, I did not review any information.

If you answered “Yes” to question #35, please answer question #36.

If you answered “No” to question #35, please proceed directly to question #48.

	Not at all	A little	Somewhat	Quite a bit	A great deal
36. Did the information help you recognize that a decision needs to be made?	1	2	3	4	5
37. Did the information prepare you to make a better decision?	1	2	3	4	5
38. Did the information help you think about the pros and cons of each option?	1	2	3	4	5

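### The decliner follow-up booklet (Appendix V) ties its skip to question 36 instead of question 35, so as printed decliners who reviewed nothing are not routed past the ten PrepDM items, as non-reviewers in the other two booklets are

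*Combined protocol and SAP*

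**What the plan says.** Section 10.1.4.1 lists PrepDM, taken from the follow-up survey, among the preparatory barriers: "The ten-item Preparation for Decision Making (PrepDM) scale was developed to evaluate decision processes". There are three follow-up booklets, and each has a filter that asks whether the woman reviewed any material before the PrepDM block begins.

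- **Appendix III (usual care).** A No answer is routed "to question #35, please proceed directly to question #48", which is past the PrepDM block.
- **Appendix IV (accepted the aid).** A woman who answers No "to questions #34 and #37, please go directly to question #51" also passes the block.
- **Appendix V (declined the aid).** A Yes answer is routed "to question #35, continue to question #36", so question 35 is the filter. Its negative option is "No, I did not review any information". The companion instruction for No, however, is "to question #36, go directly to question #48".

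The PrepDM block in Appendix V opens with "36. Did the information help you recognize that a decision needs to be made" and closes with "45. Did the information prepare you for a follow-up visit with your surgeon". Each item is rated from 1 (Not at all) to 5 (A great deal).

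**The concern.** The printed skip is keyed to an answer that question 36 does not offer, and the answer that should trigger it carries no instruction. A decliner who reviewed nothing arrives by default at ten items about information she never saw.

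Decliners stay in the analysed intervention group. Section 8.3 has them surveyed whether or not they accepted the aid, and Section 12.1.1 analyses by intention to treat. The same state, having reviewed nothing, could then yield a PrepDM score for a decliner in the intervention arm and a structural blank for a woman in usual care. The questionnaire itself would create that difference between arms.

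Section 12.1.1 models preparatory barriers as a latent mediator for co-primary objective 2. Section 12.1.4 provides multiple imputation for missing predictors but gives no not-applicable rule for skipped PrepDM items, so the analysis plan would not catch the asymmetry.

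**Working it through.** No sample size, power or alpha figure is involved. The check is to trace the printed routing for one kind of respondent, a woman who reviewed nothing, through the three booklets.

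| Booklet | PrepDM items | Printed path for a non-reviewer | PrepDM items met |
|---|---|---|---|
| Appendix III, usual care | Q36-Q45 | Q34 No, Q35 No, then Q48 | 0 |
| Appendix IV, accepted aid | Q38-Q47 | Q34 No, Q37 No, then Q51 | 0 |
| Appendix V, declined aid | Q36-Q45 | Q34 No, Q35 No, no instruction, next item Q36 | 10 |

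**Item count.** Appendices III and V: 45 - 36 + 1 = 10. Appendix IV: 47 - 38 + 1 = 10. Both match the ten-item scale in Section 10.1.4.1.

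**Which number is wrong.** Three features of the booklets show that 35 was intended. First, the Yes branch directly above is keyed to question 35. Second, Appendix III has the same structure and keys its skip to question 35, with the same target, question 48. Third, the lead-in before question 48 in Appendix V addresses all patients whether or not they reviewed anything, so questions 36-47 were meant for reviewers only. Question 46, on where the information was reviewed, cannot be answered by someone who reviewed none.

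**After correction.** With the skip keyed to No on question 35, the Appendix V path becomes Q34 No, Q35 No, then Q48. That gives 0 PrepDM items and omits Q46-Q47, as in Appendix III.

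**Route into the analysis.** Section 10.1.4.1 lists four preparatory measures: the Control Preferences Scale, PrepDM, how informed the patient feels, and SURE. Section 12.1.1 gives the latent preparatory construct three observed items and does not name them. PrepDM may or may not be among the three.

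**Related wording.** The stem of question 35 asks about receiving information in Appendix III and about reviewing it in Appendix V, although the answer options in both refer to reviewing. This does not change the routing result.

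**The case against.** The strongest reply is that nothing shows the error reached patients. Section 4.3 describes the appendix booklets as samples for reference and IRB submission, not for patient completion. Section 8.2.3 makes an emailed Qualtrics link the usual mode, and its branching is not shown. This stands: an effect on collected data is possible, not demonstrated. Paper and telephone completion are also allowed, so the fielded forms still need checking.

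A second reply is that the intent is obvious. A woman or coordinator who has just recorded that nothing was reviewed may well infer the skip, leave the items blank, or mark Not at all on question 36, read that as No and jump to question 48. This also stands, and it means nobody can say what such women would have entered.

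A reader might go further and infer that these women would all score at the floor, pulling the intervention-arm PrepDM mean down by a calculable amount and biasing the aid's estimated effect on preparation downward. The documents do not support that. They give no number of decliners who reviewed nothing, no PrepDM mean or standard deviation, and no basis for uniform floor scoring. The nearest figure, 18% in Section 1.5.1, is refusal of pilot participation, not refusal of the aid in this trial. Nor is the skipped-item comparison an unbiased benchmark. PrepDM is by design observed only in women who reviewed something, and reviewing is itself affected by the clinic sending the aid. The items also refer to the website in Appendix IV but to information generally in Appendices III and V.

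**Conclusion.** The routing error in Appendix V is established from the printed text. It is confined to intervention-arm women given the decliner booklet; acceptors who reviewed nothing are routed correctly. Whether it matters for the results rests on two conditions that the documents leave open: that the error was carried into the fielded web or paper form, and that PrepDM is one of the three preparatory items in the structural equation model. If both hold, a preparatory measure would be recorded differently by arm for women in the same situation, and this would bear on co-primary objective 2. Neither the size nor the direction of any resulting bias can be derived from the documents. The objective 1 endpoints, PEPPI-5 and active participation behaviours, do not pass through these items and are unaffected. This is a minor point, worth making because the correction is nearly free.

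**What to change.** 1. In Appendix V, change the question number in the No skip from 36 to 35.
2. Check the fielded Qualtrics branching and the ordered paper booklets for the same error.
3. If it was fielded, add one derivation rule to Section 12: PrepDM is set to not applicable for any decliner who answered No to both question 34 and question 35, matching what the skips in Appendices III and IV already produce. Both answers come before the PrepDM block, so records already collected can be identified and recoded.

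The cost is one number in a booklet, one check of the fielded forms and, if needed, one line of derivation code. No new data are required. The change makes the arms consistent in who contributes a PrepDM score. It does not remove the conditioning on having reviewed information, so a between-arm PrepDM contrast should not be read as an unbiased effect of the aid on that account alone.
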